All research activities will be performed after obtaining Institutional Review Board Approval from Emory University. A consecutive sample of women will be recruited from the FPMRS and Menopause patients within The Emory clinics. Subjects are identified after their management plan has been established to include treatment of vulvar and/or vaginal atrophy. Patients will be approached by the principal and/or co-investigators. For women that agree to participate, written informed consent will be obtained. All women who agree to participate in this study must meet inclusion criteria listed in Table 1. Once the exclusion criteria have been applied (Table 2), the qualifying subjects will be enrolled in the study. Once enrolled, each subject will complete the Female Sexual Function Index (FSFI) questionnaire and a symptom severity Likert scale. Finally, they will receive instructions on medication compliance, as well as potential adverse events for the designated medication. If we assume 50% of women offered enrollment in this study will agree and be eligible to participate, we expect to reach our target enrollment in seven to eight months.

Table 1. Inclusion Criteria
Interested in resuming or continuing sexual activity

Table 1. Inclusion Criteria

Greater than 12 months since last menstrual cycle or prior bilateral oophorectomy
40yo or older
Dyspareunia as a vulvovaginal atrophy symptom
Normal mammogram within 12 months prior to entry into the study

Table 2. Exclusion Criteria

History or suspicion of breast carcinoma
History of hormone-dependent tumor
Genital bleeding of unknown cause
Ongoing vaginal infection
History of CVA, MI or heart disease, uncontrolled HTN over 160/100
Serious disease or chronic condition that may prevent completion of study, BMI over 40
Hypercoagulable state, or currently on anticoagulant therapy
Use of any exogenous sex hormone within three months from study entry, or during the study
Pelvic surgery within the last 12 months

Randomization and Allocation Concealment

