Once a qualifying subject is identified, she will be randomized into a treatment group. The participant will be randomized to receive either a vaginal conjugated estrogens prescription or an ospemifene prescription. A computerized randomization program will be used to perform block randomization in random blocks of 4 and 10. Allocations envelopes containing the assignment will be used for the study. They will be sealed opaque envelopes with aluminum foil inside. They will also contain carbon-copy paper. The treatment number will be printed on the envelope. Once the participant has signed the informed consent form, her name will be printed on the envelope, which will transfer over to the carbon-copy paper, and the envelope will be opened.

Study Plan

The patient will be informed of her assigned medication, and she will receive a medication coupon to help offset the cost of the medication. Each medication is FDA-approved for long-term use of at least 52 weeks. For this study, a 12-week prescription for the medication will be sent electron-

[figure not shown]
ically to the pharmacy of her choice. Treatment with estrogen will consist of 0.5 gram of conjugated estrogens placed vaginally for 12 weeks. Treatment with ospemifene will consist of a 60mg tablet that will be taken at the same time daily for 12 weeks.

The patient will receive an intake packet that includes the following information:

1. Copy of signed informed consent form
2. Important contacts and instructions for emergency/adverse events
3. Allocation card
4. Medication's FDA packet insert
5. Instructions on dosing
6. 12-week date to repeat questionnaires

She will be called the following day to confirm her start date of the medication. They will return at 12 weeks and complete the same FSFI and Likert Scale questionnaires regarding sexual function and VVA symptoms. The questionnaires may also be completed over the phone with the investigator.

Alternatively, if time during clinic is limited, the patient can be consented and allocated to a medication in person, by a co-investigator. She will be called by a co-investigator on the same day to complete the enrollment and questionnaires. Below is a summary of the study plan.

Sample Size Analysis

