To our knowledge, there has been no prior study that reported the prevalence of female sexual dysfunction amongst women using vaginal conjugated estrogens, defined as having an FSFI score of 26.55 or less. With an FSD prevalence of 57%, we determine a 50% reduction in the prevalence to be clinically significant. Setting an alpha of 0.05, and a power of 0.80, and assuming a minimum of 15% dropout rate, the sample size is set to 52 in each group.

Specific Aims

Specific Aim 1: To compare the efficacy of each drug in improving sexual function.

- a. Experimental Design: In this study, participants will be asked to complete the 19-question female sexual function index (FSFI) questionnaire at the beginning of the study period and at 12 weeks. The results will be used to compare the effect of each medication on the various domains of sexual function.

The mean total score in each treatment group at baseline will be compared using Student's t-test. Additionally, the score of the components of desire, arousal, lubrication, orgasm, satisfaction and pain will be similarly compared. Later, the change in these scores between the two treatment groups at 12 weeks will be compared using a paired t-test analysis.

Anticipated Results and Interpretation: We expect to see similar results in this study, showing comparable improvements in vaginal lubrication and dyspareunia, while showing greater improvement for overall sexual health in the ospemifene group.

Potential Pitfalls, Alternative Approaches, and Future Directions: We do not anticipate any challenges with the administration and analysis of this questionnaire.

Specific Aim 2: To compare each drug's impact on VVA symptoms

- a. Experimental Design: Participants will complete a Likert scale of symptom severity at the beginning and at the end of the study. The symptoms listed will include dyspareunia, vaginal dryness, vaginal pain, and vaginal itching. The survey will ask them to rate the severity of each VVA symptom on a scale of 0 to 3, with 0 being none, 1 being mild, 2 being moderate, and 3 being severe. It will also ask them to choose their most bothersome symptom (MBS).

The mean score of the MBS in each treatment group at baseline will be compared using Student's t-test. Later, the change in score of the MBS between the two treatment groups at four weeks and again at 12 weeks will be compared using a paired t-test analysis.

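### On the alternative enrolment path the baseline FSFI, symptom ratings and choice of most bothersome symptom are taken by phone after open-label allocation, so the change scores do not start from a pre-randomisation measurement

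*Combined protocol and SAP*

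**What the plan says.** The Study Plan section describes two ways into the trial. On the alternative path, used when the clinic visit is short of time, "the patient can be consented and allocated to a medication in person, by a co-investigator". The next step is: "She will be called by a co-investigator on the same day to complete the enrollment and questionnaires". No expected share of women on this path is given.

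For women in general, the Patient Groups section says: "Once enrolled, each subject will complete the Female Sexual Function Index (FSFI) questionnaire and a symptom severity Likert scale". It continues: "Finally, they will receive instructions on medication compliance, as well as potential adverse events for the designated medication". The Randomization and Allocation Concealment section has the envelope opened once consent is signed. It does not say whether the questionnaires must be finished by then.

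The Overview under Approach states that neither participants nor clinicians can be blinded, and the Study Plan has the patient told which drug she has been assigned. Under Specific Aim 1, "The mean total score in each treatment group at baseline will be compared using" a two-sample t-test, and later "the change in these scores between the two treatment groups at 12 weeks will be compared". Specific Aim 2 treats the score of the most bothersome symptom (MBS) in the same way. The MBS is chosen on the same survey as the four symptom ratings.

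**The concern.** A change from baseline is protected by randomisation only if the baseline was fixed before the arm was known. On the alternative path it is not. A woman who has just learned that she will take a daily tablet, or use a vaginal cream, may rate her sexual function or symptoms differently because of that knowledge. The co-investigator who takes her answers by phone may know the arm too. The efficacy outcomes in both aims are self-reported, so the Overview's assurance that the data are objective does not answer this.

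The MBS adds a separate possibility. If the symptom named at baseline is the one followed to 12 weeks, then knowledge of the arm could alter which symptom is analysed as well as its starting score. Specific Aim 2 does not say whether the baseline choice is carried forward, so this part is conditional.

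**Working it through.** **1. Order of steps.** On the alternative path, the Study Plan puts consent and allocation first and the phone questionnaires second. These must be the baseline questionnaires, because they are tied to completing enrolment on the day of consent. No section requires baseline before the envelope is opened, limits use of this path, records which path was used, or plans an analysis by path. On the standard path the order is not stated. Patient Groups suggests questionnaires first, since instructions for the assigned drug come last, and the study-plan figure is not available.

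**2. What uses the baseline.** FSFI total change, FSFI domain change and MBS score change all do. The sample size rests on the prevalence of sexual dysfunction (FSFI 26.55 or less). A comparison of that prevalence at 12 weeks would use no baseline value.

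**3. Group size.** From Sample Size Analysis: p1 = 0.57, p2 = 0.57 × 0.5 = 0.285, alpha 0.05 (two-sided assumed), power 0.80, dropout 15%. With unpooled variance, n = (1.960 + 0.842)² × (0.57 × 0.43 + 0.285 × 0.715) / 0.285² = 7.85 × 0.4489 / 0.0812 = 43.4, so 44. Then 44 / 0.85 = 51.8, so 52 per arm. The stated figure is reproduced and this point does not change it.

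**4. Would the planned baseline t-test reveal a shift?** Let d be the between-arm shift in baseline answers caused by knowing the arm, in SD units, and f the share of women on this path. Neither is in the documents; both are assumed here. The shift in the arm means is f × d, and the non-centrality is f × d × √(52/2) = 5.10 × f × d, with 102 degrees of freedom and a two-sided 5% test.

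| d | f = 25% | f = 50% | f = 100% |
|---|---|---|---|
| 0.2 | 5.7% | 8.0% | 17.3% |
| 0.3 | 6.7% | 11.8% | 32.9% |

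The test would usually miss a shift of this order. A significant result could not be told from chance imbalance.

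**5. What cannot be computed.** Let k be the fraction of d still present in answers at 12 weeks, when every woman knows her arm. The post-allocation baseline adds −f × d to the arm difference in change and 12-week reporting adds +k × d, so the net is d × (k − f). With baseline taken before allocation, f = 0 and the net is d × k. For d = 0.2 and f = 50%:

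- k = 0: −0.10 becomes 0.
- k = 0.5: 0 becomes +0.10.
- k = 1: +0.10 becomes +0.20.

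For k of zero or more, absolute bias in the change score falls only when f exceeds 2k. If the shift reversed sign by 12 weeks (k below 0), the two parts would add and the fix would help. With d, f and k all unknown, this algebra gives no size for the bias and is not evidence that the fix lowers its total.

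**The case against.** The strongest reply is that the trial is open-label at 12 weeks in any case, and that a reporting shift lasting from baseline to 12 weeks cancels in the change score of these women. Taking baseline before allocation would remove that cancellation. This stands, as step 5 shows. It does not justify the present order: exact cancellation across the trial needs k to equal f, which nobody has planned or can verify. A pre-allocation baseline leaves one known limitation, at 12 weeks, in place of two that interact.

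It can also be said that this path is an exception and its effect may be small. That is fair. With d = 0.2, f = 25%, 44 evaluable per arm and a baseline-to-12-week correlation of 0.5, the change score has SD 1 and the arm difference a standard error of √(2/44) = 0.213. The baseline part is 0.25 × 0.2 = 0.05 SD, or 0.23 standard errors.

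A reader might infer more than the documents support:

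- **That the results will be biased towards ospemifene.** The stated expectation favours ospemifene, but nothing shows that a shift occurs or in which direction.
- **That the standard path has the same flaw, or is clearly free of it.** The order there is not stated, so neither can be claimed.
- **That the drug has already acted when baseline is taken.** The questionnaires are taken on the day of allocation, and the Study Plan's standard sequence says: "She will be called the following day to confirm her start date of the medication". An early drug effect is therefore unlikely, though not expressly excluded.

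**Conclusion.** The point holds in a limited form. Followed as written, the alternative path gives a baseline recorded after an unblinded allocation, and the FSFI and MBS change scores rest on it. The order of steps is explicit in the text. The importance of the problem is unknown, because the documents give neither the share of women affected nor the size or direction of any shift. The dependence of the MBS endpoint on the arm is conditional on the baseline choice being the one followed. A 12-week prevalence comparison alone is outside the problem.

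The one firm figure is the weakness of the intended check: about 17% power for an assumed 0.2 SD shift even if all women used this path, and 5.7% if a quarter did. It would be wrong to conclude that reordering the steps is shown to reduce total bias in the change score. The case for it is that it restores a true pre-randomisation baseline at little cost.

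**What to change.** State for both paths that eligibility is confirmed, and that the FSFI, the symptom ratings and the MBS choice are completed and dated, before the allocation envelope is opened. When clinic time is short, the woman self-completes them in clinic before opening: 19 FSFI items, four ratings and one MBS choice, 24 responses in all. Opening the envelope later, after questionnaires taken by phone, would also give a pre-allocation baseline. It is less attractive because she would no longer be present at the opening.

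Record the enrolment path before opening. If any baseline is still taken after allocation, add a sensitivity analysis defined by that recorded path, not by when the questionnaire happened to be completed. State in Specific Aim 2 whether the baseline MBS is the symptom followed to 12 weeks.

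The cost is protocol wording, one recorded field and a few more clinic minutes, with no extra visit and no change in sample size. The sensitivity analysis loses precision, with the standard error multiplied by 1/√(1 − f). Leaving out 25% of women (44 to 33 per arm) raises it by about 15%, and leaving out 50% (22 per arm) by about 41%. Unblinded self-report at 12 weeks remains, and a reporting shift that persists to 12 weeks would no longer cancel in the change score; the report should state this as a limitation.

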In 2013, Ospemifene was approved by the Food and Drug Administration for the treatment of moderate to severe dyspareunia that is due to menopause [10]. Ospemifene is a non-estrogen selective estrogen receptor modulator (SERM). SERMs are estrogen receptor (ER) agonist/antagonists that typically induce the desirable effects of estrogen while avoiding estrogen-related adverse effects. Unlike other drugs in this class, Ospemifene has been shown to have significant estrogenic agonist effects on the vagina and bone, but antagonist effects on breast tissue [6]. Furthermore, it significantly improves overall sexual function [12]. Despite this promising medical profile, it remains a second or third line of therapy to treat VVA. More research is needed to determine if ospemifene is an acceptable, and possibly a favorable, alternative to vaginal estrogen for the treatment of vulvovaginal atrophy, especially if there is any concern for sexual function. In this research study, we aspire to determine the efficacy of ospemifene compared to a vaginal estrogen. The primary aim of this research is to compare female sexual function as measured by a validated instrument in women randomized to receive ospemifene and vaginal estrogen. Secondary aims include comparing markers of vaginal health and safety in both treatment groups.

Hypothesis

Ospemifene is a nonhormonal alternative that has proven to significantly improve sexual health and vulvovaginal atrophy, yet vaginal estrogen is still considered the first-line therapy. Our null hypothesis is that ospemifene has a similar efficacy as vaginal conjugated estrogens for improving sexual function in postmenopausal women who have vulvovaginal atrophy.

Specific Aims

Specific Aim 1: *To compare the efficacy of ospemifene and vaginal conjugated estrogens on female sexual function.* Ospemifene is the only non-estrogen that is FDA-approved to treat dyspareunia in postmenopausal women. Further, studies report a significant improvement in sexual health in patients that are treated with ospemifene [12]. However, vaginal estrogen therapy (with conjugated equine estrogen or estradiol) remains the most commonly prescribed treatment for dyspareunia. To our knowledge, a direct comparison of ospemifene and local vaginal estrogen therapy on postmenopausal female sexual function has not been performed. We hypothesize that ospemifene provides a greater improvement in sexual function in postmenopausal women with dyspareunia and VVA.

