Specific Aim 2: *To compare the effects of ospemifene and vaginal conjugated estrogens on symptoms of VVA.* We hypothesize that treatment with either ospemifene or vaginal conjugated

estrogens will demonstrate comparable improvements in VVA symptoms. In the population randomly treated with vaginal conjugated estrogens or ospemifene in specific aim 1, we will compare the change from baseline and between groups.

Significance

Female Sexual Dysfunction

Traditionally, female sexual dysfunction (FSD) is defined as the disorder of desire, arousal, pain and/or muted orgasm in women [28]. While many people may consider this disorder to be pertinent only during reproductive years, it is very common in the menopausal women population, affecting 57% of women in menopause [5]. In 2014, Nappi et al published a review of data that shows the importance of discussing sexual function and vaginal atrophy with postmenopausal women. 1 in 5 women over the age of 70 still engage in intercourse. Moreover, 71% of women agree that, "it was important to them to maintain an active sex life." The article also adds that only 3% of women will seek advice about sexual function if not prompted. Many who do bring this problem to their provider's attention feel as though it is dismissed. Meanwhile, providers tended not to proactively address sexual health for middle and later life-aged women, because of time constraints, inadequate training, personal attitudes and beliefs that sex is not a priority for older patients [29].

What is Vulvovaginal Atrophy?

There is significant overlap between FSD and VVA. Women with FSD are almost 4 times as likely to have VVA [29]. Once a woman reaches menopause, her ovarian production of estrogen decreases dramatically. The vagina and vulva are two organs that are affected by the lack of estradiol in the body. Without estrogen, the vagina epithelial cells decline in maturation, and there is also an increase in the vaginal pH. These changes lead to the common symptoms of painful intercourse, vaginal dryness, pain, and itching. They also put the vaginal epithelium at risk for infection and inflammation. Further, the increase in pH is associated with an increased rate of recurrent urinary tract infections in postmenopausal women [13]. In the US, approximately 60% of women report symptoms related to vulvovaginal atrophy [4].

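### The 52 per arm rests on a comparison of FSD prevalence that no planned analysis makes, so the stated 80% power belongs to no planned test

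*Combined protocol and SAP*

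**What the plan says.** The Introduction gives the main objective: "The primary aim of this research is to compare female sexual function as measured by a validated instrument". It mentions no cutoff.

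The Sample Size Analysis uses a binary outcome, FSD, defined as an FSFI score of 26.55 or less. It states: "With an FSD prevalence of 57%, we determine a 50% reduction in the prevalence to be clinically significant". It continues "Setting an alpha of 0.05, and a power of 0.80, and assuming a minimum of 15% dropout rate" and arrives at 52 per group, 104 in all. It also explains that, to the authors' knowledge, "there has been no prior study that reported the prevalence of female sexual dysfunction amongst women using vaginal conjugated estrogens". The 57% is therefore a stand-in. The Significance section describes FSD as "affecting 57% of women in menopause", which is a general figure and not one for treated women.

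The planned analyses are in the Specific Aims that follow. For Aim 1 (FSFI total and six domain scores): "Later, the change in these scores between the two treatment groups at 12 weeks will be compared using a paired t-test analysis". For Aim 2, on a 0 to 3 symptom scale: "the change in score of the MBS between the two treatment groups at four weeks and again at 12 weeks will be compared". The 26.55 cutoff appears only in the sample-size paragraph, and no test or estimate of the proportion below it is planned.

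**The concern.** A power statement describes one test of one endpoint. Here the endpoint used for sizing (a proportion) and the endpoints analysed (mean scores) differ, so two things are lost.

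- The main comparison, FSFI change between arms, has no stated power and no stated detectable difference. A reader could easily attach the 80% to it. A null result would then be judged against a figure that does not apply.
- The only effect the authors call clinically significant, a halving of FSD prevalence, is not set down for estimation. It can be computed from the FSFI totals already collected. If it is added after the results are known, it becomes a post hoc analysis of the very effect the trial was sized on. The trial is open-label with a self-reported outcome, no single primary endpoint is named, and Aim 1 alone offers seven scores.

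**Working it through.** **Inputs from the Sample Size Analysis.** p1 = 0.57; halving gives p2 = 0.285; alpha 0.05; power 0.80; dropout 15%; stated N 52 per arm. Sidedness and formula are not stated.

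**1. Reproducing the 52.** Two independent proportions, two-sided, unpooled variance:

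n = (1.960 + 0.842)² × [p1(1−p1) + p2(1−p2)] / (p1−p2)²

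= 7.849 × (0.2451 + 0.2038) / 0.0812 = 43.4, so 44 evaluable per arm. Then 44/0.85 = 51.8, so 52.

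This matches exactly. Other versions do not: the pooled two-sided formula gives 47, or 56 after dropout; the arcsine formula gives 46, or 55. The pooled one-sided formula with continuity correction comes close, at 43, or 51.

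**2. Is that comparison planned?**

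| Place | Quantity | Method |
|---|---|---|
| Sample Size Analysis | Proportion with FSFI 26.55 or less | Not named; reproduces as two proportions |
| Aim 1 | FSFI total and six domains, baseline and change | t-tests |
| Aim 2 | MBS score, baseline and change | t-tests |

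No analysis row contains the quantity in the first row.

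**3. What 44 per arm gives for scores.** All figures are two-sided at 0.05 with 80% power, in units of the 12-week FSFI SD. For a two-sample t-test of 12-week totals the detectable difference is 0.604 SD. Let r be the correlation between baseline and 12-week scores. The documents give none, so a range is assumed, with equal SDs at both times.

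| r (assumed) | Baseline-adjusted: 0.604 × √(1−r²) | Change score: 0.604 × √(2(1−r)) |
|---|---|---|
| 0.2 | 0.59 | 0.76 |
| 0.5 | 0.52 | 0.60 |
| 0.7 | 0.43 | 0.47 |

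The change score is the planned quantity. What it can detect depends heavily on an r that is not given.

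**4. What 44 per arm gives for the proportion.** Chi-square power by full binomial enumeration, without continuity correction, the other arm halved. Control rates other than 57% are assumptions.

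| Control rate | 40% | 45% | 50% | 57% | 65% | 70% |
|---|---|---|---|---|---|---|
| Power | 55% | 63% | 70% | 78% | 86% | 91% |

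The direction of error in the 57% is unknown. Entry requires "Dyspareunia as a vulvovaginal atrophy symptom", which points to a higher rate than in menopausal women generally. Twelve weeks of active treatment points to a lower one.

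**5. Expected precision.** 95% CI half-width for the risk difference: 1.96 × √(0.4489/44) = 0.198, about 20 percentage points. For the unadjusted FSFI difference: 1.988 × √(2/44) = 0.42 SD.

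**The case against.** The strongest reply is that both endpoints come from the same FSFI total, so sizing on the proportion may cover the score comparison. If scores are normal with equal SDs, 57% versus 28.5% below one cutoff is a shift of 0.176 + 0.568 = 0.74 SD. A t-test of 12-week totals with 44 per arm has 93% power for that shift. For the change score the power is 78% at r = 0.2, 93% at r = 0.5 and 99% at r = 0.7. This stands as arithmetic, and it is why the point is not that the trial is too small. But the documents make neither the normality assumption nor the conversion. Power also falls quickly for smaller shifts: about 64% at 0.5 SD and 46% at 0.4 SD.

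Three lesser objections have some force.

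- The between-arm reading and the 28.5% are inferred, not stated. The exact match in step 1 supports them. If a fall from baseline was meant instead, the planned analyses still do not use prevalence.
- The gap between 78% and 80% reflects choice of formula, not an error in the plan.
- The 0.60 SD is solved backwards from a fixed N, so it is not itself a clinically argued target. That is correct, and the team would have to supply the argument.

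**Conclusion.** The concern holds. The 52 per arm is sound arithmetic for a comparison of 57% with 28.5%, but that comparison is not in the analysis plan, and the analyses that are planned carry no power statement. This should be put right before any results are seen.

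The consequence is a gap in specification, not demonstrated low power. The score comparison has 80% power at about 0.60 SD for 12-week totals, or between 0.47 and 0.76 SD for the planned change score as r runs from 0.7 down to 0.2. Whether such differences are plausible or important cannot be judged from the documents, which give no FSFI SD, correlation or target difference. The figures assume 44 evaluable women per arm and two-sided testing. The SD-based ones also assume equal SDs.

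**What to change.** Keep 104 women and name one primary endpoint whose analysis matches the power statement. Either of these would do.

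- **(a) Score as primary.** Name the 12-week FSFI total, compared between independent arms and adjusted for baseline. Restate the sample size along these lines: 52 per arm, 44 evaluable after 15% dropout, gives 80% power at two-sided alpha 0.05 for a 0.60 SD difference in FSFI total, or 0.52 SD with baseline adjustment if the baseline to 12-week correlation is 0.5 (an assumption). Give the FSFI SD assumed and say why a difference of that size matters clinically. Prespecify the proportion with FSFI 26.55 or less at 12 weeks as key secondary, as a risk difference with 95% CI.
- **(b) Proportion as primary.** Name the proportion with FSFI 26.55 or less at 12 weeks, compared between arms by chi-square. Restate power as about 78% for 57% versus 28.5%, with the range 55% to 91% for control rates of 40% to 70%. The FSFI score comparison becomes secondary.

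Option (a) stays closer to Aim 1 as written. Option (b) keeps the effect already called clinically significant, but makes a dichotomised score primary.

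Neither needs more women, visits or data; the work is a rewritten sample-size paragraph and one prespecified analysis. The price is a 0.60 SD difference to justify under (a), or a slightly lower stated power and a demoted score comparison under (b).

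### FSFI is compared as unadjusted change and baseline scores are significance-tested; adjusting for baseline FSFI would give equal or better precision at no cost in patients

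*Combined protocol and SAP*

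**What the plan says.** The second Specific Aims section (after Sample Size Analysis) gives the whole analysis of FSFI. Under Specific Aim 1, "The mean total score in each treatment group at baseline will be compared using Student's t-test", and the six domain scores are treated in the same way. Afterwards "the change in these scores between the two treatment groups at 12 weeks will be compared", with a paired t-test named as the method. Under Specific Aim 2, "The mean score of the MBS in each treatment group at baseline will be compared using Student's t-test", again followed by a comparison of change with a paired t-test.

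No covariate, regression model or ANCOVA is mentioned in the document. Randomization and Allocation Concealment describes blocks of 4 and 10, with no stratification by baseline FSFI. The Introduction makes sexual function on a validated instrument the primary aim, but no primary endpoint is formally designated.

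Sample Size Analysis rests on a different quantity, the prevalence of female sexual dysfunction, "defined as having an FSFI score of 26.55 or less". The effect sought there is a halving of an assumed 57%. Error rates and attrition are then given as "Setting an alpha of 0.05, and a power of 0.80, and assuming a minimum of 15% dropout rate", arriving at 52 per group.

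Study Plan adds an alternative pathway in which a woman consents and is allocated in clinic, then is telephoned later the same day to complete the questionnaires. Overview says that treatment is not blinded.

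**The concern.** There are two linked issues.

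First, the baseline tests serve no purpose. There are eight: FSFI total, six domains and the most bothersome symptom. When baseline is recorded before allocation, any difference between randomised arms is due to chance, and the plan attaches no action to the result. A non-significant test does not show that the arms are close enough for imbalance to be harmless.

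Second, change from baseline is an inefficient way to use the baseline score. Subtracting it in full treats the slope of 12-week score on baseline as 1. When the slope is below 1, an arm that happens to start lower tends to show more improvement through regression to the mean. ANCOVA estimates the slope from the data.

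At stake is the precision of the main FSFI comparison. The baseline score is already collected from every woman, so the precision can be recovered by analysis wording alone.

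**Working it through.** **Inputs from the document.** Alpha 0.05 and power 0.80; sidedness is not stated and is taken as two-sided. Prevalence 57% against 28.5% (half of 57%). Dropout 15%. 52 per group.

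**Inputs assumed.** The document gives no FSFI standard deviation (SD) and no correlation (rho) between baseline and 12 weeks. I use rho from 0.3 to 0.8 and, except in step 4, the same SD at both visits. Results are in units of that SD.

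**1. The plan's own figure.** Two proportions, two-sided, unpooled variance:

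n = (1.960 + 0.842)² × [0.57 × 0.43 + 0.285 × 0.715] / (0.57 − 0.285)² = 7.849 × 0.4489 / 0.0812 = 43.4, rounded up to 44.

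44 / (1 − 0.15) = 51.8, rounded up to 52. The stated figure is reproduced, with about 44 completers per arm. It rests on a binary outcome, so nothing below alters it.

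**2. Precision with equal SDs.** Per woman, in units of SD²:

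- Change score: 2(1 − rho)
- ANCOVA: 1 − rho²
- Ratio, ANCOVA to change: (1 + rho)/2

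The difference detectable with 44 per arm at 80% power is 2.802 × √(2/44) = 0.597, multiplied by √[2(1 − rho)] for change or √(1 − rho²) for ANCOVA. Where change has 80% power, ANCOVA has Φ(2.802 × √[2/(1 + rho)] − 1.960).

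| rho | Variance ratio | Detectable, change (SD) | Detectable, ANCOVA (SD) | ANCOVA power where change has 80% |
|---|---|---|---|---|
| 0.3 | 0.65 | 0.71 | 0.57 | 94% |
| 0.5 | 0.75 | 0.60 | 0.52 | 90% |
| 0.7 | 0.85 | 0.46 | 0.43 | 86% |
| 0.8 | 0.90 | 0.38 | 0.36 | 84% |

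ANCOVA spends one degree of freedom on the slope, which costs about 1% of variance and is ignored in the table.

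**3. Chance imbalance.** If the arms differ at baseline by D, the change-score contrast shifts by −(1 − rho)D. A comparison of 12-week scores alone would shift by +rho × D, and ANCOVA by 0. The standard error of D with 44 per arm is √(2/44) = 0.213 SD, so the baseline t-test flags only imbalances above about 0.42 SD. An unflagged D of 0.3 SD at rho 0.5 shifts the change contrast by 0.5 × 0.3 = 0.15 SD in absolute size.

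This is not additional to step 2. Algebraically, 2(1 − rho) = (1 − rho²) + (1 − rho)². The second term, (1 − rho)², is the variance produced by chance imbalance passing through the shift. The extra variance and the conditional shift are one loss seen in two ways.

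**4. Without equal SDs.** Let s0 and s1 be the SDs at baseline and 12 weeks.

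- Change: s0² + s1² − 2 × rho × s0 × s1
- ANCOVA: s1²(1 − rho²)
- Difference, change minus ANCOVA: (s0 − rho × s1)², which is never negative

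The direction therefore holds for any SDs, but the size does not. With rho = 0.7 and s1 = 1.4 × s0, the slope is 0.98. In units of s0², change has variance 1 + 1.96 − 1.96 = 1.00 and ANCOVA has 1.96 × 0.51 = 1.00, so there is essentially no gain.

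**The case against.** The strongest reply is that nothing here is invalid. A two-sample comparison of change is unbiased over randomisation, and its standard error already includes the effect of chance imbalance. A D of 0.3 SD is about 1.4 standard errors (0.3 / 0.213), roughly a one-in-six event. The resulting 0.15 SD shift is about 0.7 of the standard error of the change contrast at rho 0.5. All of this stands, and it makes the point one of efficiency.

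A reader might infer more than the document supports:

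- *That baseline FSFI is used only in a significance test and imbalance is ignored.* Baseline is subtracted in every change score, so imbalance is over-corrected.
- *That noise and bias are two separate harms.* Step 3 shows that they are the same loss.
- *That the gain is known.* It depends on SDs and a correlation that the document does not give, and it can be close to zero.
- *That the trial is the wrong size for this reason.* The 52 per arm comes from a prevalence comparison.

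It can also be said that naming a paired t-test for two independent arms is the larger defect in the same sentence. That is right, but replacing it with a two-sample t-test on change would leave the present point untouched, whereas ANCOVA settles both.

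Two objections bear on the remedy. In the telephone pathway a woman may answer the baseline FSFI after learning her open-label treatment. For her it is not a clean pre-randomisation covariate, and a difference between arms need not be chance. The change score has the same weakness, so this argues for fixing the order of collection rather than for keeping change scores. The other objection is that a linear model of a 0 to 3 symptom rating is approximate. The planned t-tests on mean ratings make the same approximation.

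**Conclusion.** The point holds as a free improvement. The plan compares unadjusted change and runs eight baseline tests that lead nowhere, while a covariate already collected goes unused as one. Apart from about one degree of freedom, adjusting for baseline cannot be less precise, whatever the SDs.

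With equal SDs at both visits, an assumption, the variance saving is 35%, 25%, 15% and 10% at rho 0.3, 0.5, 0.7 and 0.8. It may vanish if the 12-week SD exceeds the baseline SD and rho is high. The detectable differences further assume that the 44 completers per arm implied by the binary calculation supply the FSFI means.

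The document does not support calling the change comparison biased over randomisation, nor revising the sample size on this ground. Treating the FSFI mean comparison as the main analysis is an inference from the stated primary aim, since no endpoint is designated and no analysis of the prevalence is described.

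**What to change.** 1. In Specific Aim 1, replace the change-score comparison and its paired t-test. Proposed wording: *FSFI total at 12 weeks will be analysed by a linear model with treatment arm and baseline FSFI total as terms; the adjusted difference between arms will be reported with its 95% confidence interval.*
2. Use the same model, each with its own baseline, for the six FSFI domains. In Specific Aim 2, use it for the score of the symptom that the woman chose as most bothersome at baseline.
3. Delete the eight baseline t-tests and summarise baseline by arm without p-values.
4. In Study Plan and in Randomization and Allocation Concealment, require every woman to complete the baseline questionnaires before her envelope is opened, including in the same-day telephone pathway.

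Items 1 to 3 cost a few sentences, with no added patients or data. Item 4 needs a change to the order of enrolment steps: where clinic time is short, allocation has to wait until the questionnaires are done.
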